24. BIOLOGICAL MATERIALS TRANSFER AGREEMENT

Not applicable.

25. INVESTIGATIONAL DRUG FACT SHEET AND IND/IDE HOLDER

Drug Names: Bromocriptine mesylate; Amisulpride

IND #: 191908

IND holder: [name]

[name] and the Lab Manager will be responsible for monitoring the study in the following ways:

Medication Handling and Storage

- Per 21CFR §312.6 Labeling of an investigational new drug, medications will be stored in a locked cabinet in the research office of the PI. That office is embedded in the UCSD Eating Disorder Research Program office suite, which is locked. Each study drug will be labeled with the statement “Caution: New Drug—Limited by Federal (or United States) law to investigational use.”
- Per 21CFR §312.61 Control of the investigational drug, the investigator will not supply the investigational drug to any person not authorized under this part to receive it.

Subject Level

- [name] will review all Pre-Scan Blood Test and EKG results to ensure subject's medication risks are minimized.
- Research staff will complete symptom checklist on each Study Visit day and will document the following: Documentation of blood pressure & heart rate pre-medication administration and post scan; symptom checklist including: nausea, headache, dizziness, tiredness, other. Research Staff will report these values to [name] and the Lab Manager at the end of the Study Visit.
- Research staff will contact [name] and/or Lab Manager via phone if there is a significant drop in blood pressure (20 or more points systolic) after the medication administration or significant symptoms that the subject feels keep her from continuing the study.
- [name] or Lab Manager will confirm with research team that all unexpected or adverse events (AEs/SAEs) have been reported to the IRB and FDA in the required timeframe.
- [name] or Lab Manager will review each subject folder after the subject completes the study to ensure required documentation and procedures have been completed.

Study Level

- The Lab Manager will prepare monthly aggregate reports of the adverse events, serious adverse events, and unexpected events and will review with [name].
- [name] will review monthly aggregate reports to determine safety of the study medications and whether the study is safe to be continued.

Per FDA Approval, [name] will be responsible for the following reporting requirements:

- [name] will report any unexpected fatal or life-threatening suspected adverse reactions to FDA no later than 7 calendar days after initial receipt of the information.
- [name] will report any 1) serious, unexpected suspected adverse reactions, (2) findings from other clinical, animal, or in-vitro studies that suggest significant human risk, and (3) a clinically important increase in the rate of a serious suspected adverse reaction to FDA no later than 15 calendar days after determining that the information qualifies for reporting.
- [name] will submit annual progress reports within 60 days of the anniversary of the date that the IND became active.

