Alternatively, subjects may complete the Electrocardiogram (EKG) at Medical Care San Diego ([name]) and the labs (Creatinine, BUN, electrolytes and serum pregnancy test) at either the Medical Care San Diego ([name]) or a LabCorp location close to where the subject resides. Subjects who use these facilities to complete the EKG and labs will provide the PI and his staff with the test results. Subjects will need to complete these tests no more than one week prior to the first scheduled MRI scan. The research study will pay these facilities directly on the subject's behalf with the self-pay option. Once the PI receives the test results, if he feels the results are out of range he may withdraw the subject from the study.

Study Visit 1

Location: Sharp and Children's MRI Center ([name])

The morning of the imaging procedures the subject will go to the Sharp and Children's MRI Center for the scanning procedures. The medication will need to be administered 3 hours before the start of the scan.

When the subject arrives at the MRI Center, subjects will complete a urine pregnancy test. After the pregnancy test (test must be negative), the research assistant will take the subject's blood pressure and measure her heart rate and administer the study medication. The subject will complete the Taste Labeled Magnitude Scale, Hedonic Taste Preference Scale, Food Cravings Questionnaire (State), Eating Disorders Examination (EDE-Q), Temporal Experience of Pleasure Scale (TEPS), Eating Expectancy Inventory (EEI), Beck Depression Inventory (BDI-II), The Positive and Negative Affect Schedule (PANAS), and eat a standardized breakfast.

The research staff will then review study procedures and fMRI tasks.

Subjects will then complete the fMRI and structural MRI (details of tasks outlined below).

After the scan, the research assistant will take the subject's blood pressure and heart rate and will have the subject complete the Post Scan Pleasantness Ratings and the Post MRI Questionnaire.

The total length of the study visit will be approximately 4 hours (3 hours pre-scan, 1 hour scan).

Study Visit 2

Location: Sharp and Children's MRI Center ([name])

The morning of the imaging procedures the subject will go to the Sharp and Children's MRI Center for the scanning procedures. The medication will need to be administered 3 hours before the start of the scan.

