Amisulpride. Amisulpride (4-amino-N-[(1-ethylpyrrolidin-2-yl)methyl]-5-ethylsulfonyl-2-methoxy-benzamide has a bioavailability of 48% and a half-life of about 12 hours (Rosenzweig et al., 2002). It binds selectively (<https://pubchem.ncbi.nlm.nih.gov/compound/2159>) to DA D(2) and D(3) receptors in the limbic system. It reaches its peak plasma levels after 1 hour and has a second peak after 3 hours. Amisulpride does not have active metabolites (Bergemann et al., 2005). Low doses of amisulpride block presynaptic D(2)/D(3)-dopamine autoreceptors, thereby enhancing dopaminergic transmission, whereas higher doses block post-synaptic receptors, thus inhibiting DA activity (Leucht et al., 2002). In this application, we will apply a high dose to take advantage of the DA D2 receptor blocking effects of amisulpride. We are orienting our dosing on previous research using a single dose of 400mg amisulpride to block post-synaptic DA D2 receptors during fMRI (Kahnt and Tobler, 2017). That dosage showed good tolerability (Rosenzweig et al., 2002). Whether this dose is tolerable in an AN population has not been established and is a goal of this study. Establishing pharmacokinetics with plasma levels will also be important but will be part of future larger studies.

Bromocriptine. Bromocriptine is a semisynthetic, ergot alkaloid with anti-Parkinson and lactation inhibitory activities. Bromocriptine selectively binds to and activates postsynaptic DA D2-like receptors in the central nervous system (CNS), its half-life is between 2 and 8 hours, and it does not have active metabolites (<https://pubchem.ncbi.nlm.nih.gov/compound/31101>). Bromocriptine has a bioavailability of 28% and reaches its peak plasma level around 3 hours after ingestion (Holt et al., 2010). Bromocriptine has been used in fMRI previously and modulated reward and reversal learning (Cools et al., 2009). Effects of DA synthesis capacity will be tested in future larger studies. We will apply a single dose of 1.25mg bromocriptine, which was effective in manipulating both fMRI and behavior results (Cools et al., 2009; Lissek et al., 2018).

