Special Pharmacological Considerations. Bromocriptine is an anti-Parkinson medication available in the US. An investigational new drug (IND) application to the Federal Drug Administration (FDA) has been approved, IND # 141908. Amisulpride is an antipsychotic not freely available in the US; however, it can be purchased via Sanofi France as in previous studies (Admon et al., 2017). We have received an IND from the FDA, which allows for legal import of amisulpride. Both medications have a plasma peak of 3 hours, and fMRI will begin for all sessions at that time point after taking active drug or placebo. The half-lives for amisulpride of 12 hours, and 2-8 hours for bromocriptine are short enough to allow 3 days in between studies to suffice the 5 half-lives

rule for medication elimination from the body (neither medication has active metabolites) (Bergemann et al., 2005; Holt et al., 2010; Schatzberg and Nemeroff, 2013).

Handling of Study Medication

Storage Location: UC San Diego Health Eating Disorders Center for Treatment and Research, [name] (PI Office, [name])

Medications will be stored in a locked cabinet in the research office of the PI. That office is embedded in the UC San Diego Health Eating Disorders Research Program office suite, which is locked. Each study drug will be labeled with the statement “Caution: New Drug—Limited by Federal (or United States) law to investigational use.” (§312.6 Labeling of an investigational new drug.).

A randomization protocol will be developed ahead of the study using Research Randomizer (<https://www.randomizer.org>). The PI will randomize the study days for the three medications. A master file with the randomization of medication per subject will be kept by the study monitor ([name]).

While the tablets look slightly different, subjects will not be told what type of medication they receive on either day. Study participants have been drug naïve to any of the study medications, and we do not expect recognition. It is uncertain what specific effects each medication will have on brain function and there will therefore be no implicit bias.

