The feasibility procedures will also include assessment of side effects from the medication. In case a study participant was to have a serious reaction (such as anaphylaxis) 911 would be called immediately and the person transported to the medical emergency room that is located about 500 yards away on campus. The study personnel are trained in basic life support.

Cardiac conduction abnormalities have been noted in individuals with anorexia nervosa. To ensure patient safety, we will only include patients in our study that are considered medically stable by the Medical Director at UC San Diego Health Eating Disorders Center for Treatment and Research (i.e. normal EKG and lab electrolyte values). If the staff at those facilities does not feel their patient is stable enough to complete the fMRI scan, the study will be postponed until she is stable, or the patient will be withdrawn from the study if timing does not allow the scan to be postponed. Study participants will have their blood pressure and heart rate taken prior to study drug administration as well as at the end of each study day. In case there is a significant drop in blood pressure indicating orthostasis during the study or due to the study medication, we will keep study participants in our research space and provide them with fluids and will recheck the blood pressure until

it has normalized. In case there were ongoing indication of orthostasis we will refer the participant to the local emergency room on campus.

Electrocardiogram. The risk is minimal. Any skin irritation from the electrode placement usually lessens within a few minutes of removing the electrode.

Data and Safety Monitoring Plan

Data will be analyzed as above for brain imaging data. The behavioral data will be analyzed using SPSS statistical software on password protected computers. The PI will perform data analysis with some research assistant support.

Subjects will be continuously monitored during their study participation by asking about how subjects feel and if they have any problems while in the study. However, in case of unexpected effects, the PI will report those to UCSD HRPP.

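### The only side-effect record with a defined time point closes about 4 hours after dosing; no look-back question or contact after Visit 3 is scheduled, although tolerability in anorexia nervosa is a stated goal

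*Combined protocol and SAP*

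**What the plan says.** Section 25 (Subject Level) defines the side-effect record: "Research staff will complete symptom checklist on each Study Visit day". The form covers nausea, dizziness, headache and tiredness, plus an open category. Staff pass the results on "at the end of the Study Visit". Section 15 has "blood pressure and heart rate taken prior to study drug administration as well as at the end of each study day".

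Section 9 sets the timing for each study visit: "The medication will need to be administered 3 hours before the start of the scan". It gives the visit as roughly 4 hours, of which the scan takes one. Both procedures charts in section 9 end at Study Visit 3.

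On pharmacology, section 9 says that amisulpride "has a bioavailability of 48% and a half-life of about 12 hours", gives bromocriptine 2 to 8 hours, and argues: "The half-lives for amisulpride of 12 hours, and 2-8 hours for bromocriptine are short enough to allow 3 days in between studies". The yardstick there is five half-lives.

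On purpose, section 9 says of amisulpride: "Whether this dose is tolerable in an AN population has not been established and is a goal of this study". Section 7 asks whether both challenge drugs are tolerated in this population, and section 15 makes side-effect assessment part of feasibility.

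There are also general statements. Section 11 promises that well-being is monitored through the study. Section 15 promises a check on well-being after dosing and regular questions about problems during participation. Section 16 lists a medication effects log among the papers to be filed. None of these carries a time point.

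**The concern.** The collection window limits what can be concluded about tolerability. If it closes while much of the drug is still present, a symptom that starts that evening or the next day reaches the data only if the participant raises it unprompted.

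Two things follow in a three-period crossover. First, a symptom mentioned at the next visit could be entered on that day's form and so counted against the next drug, because no question ties it back to the previous dose. Second, after the third dose there is no next visit, so even that chance is gone.

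Both problems work against the tolerability goal, since missed symptoms make a drug look better tolerated than it is. They also bear on the monthly safety review in section 25, so far as it draws on these forms. Section 15 says that there is no independent monitoring board.

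**Working it through.** **Inputs, all from the protocol.** Dose to scan, 3 h; scan, 1 h (section 9, Study Visits 1 to 3). Half-lives, about 12 h for amisulpride and 2 to 8 h for bromocriptine; amisulpride peaks at 1 h and again at 3 h, bromocriptine at about 3 h (section 9, drug descriptions). Gap between scans, 3 days, with 2 to 4 allowed (section 9). Six orders (section 9). Completers, 44 (section 10).

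**The plan's own figure.** Five half-lives are 5 × 12 = 60 h for amisulpride, and 5 × 2 = 10 h to 5 × 8 = 40 h for bromocriptine. Three days are 72 h, so the stated 3-day gap meets the rule for both drugs. (The permitted 2-day gap is 48 h, or 48/12 = 4 amisulpride half-lives, short of 60 h. That is a separate matter, and those statements in section 9 need to be reconciled.)

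**When the record closes.** 3 + 1 = 4 h after dosing. The tasks fit the scan hour: 28.5 + 3 × 8.5 = 54 min.

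**Hours of the five half-lives left after the visit.** Amisulpride: 60 − 4 = 56 h. Bromocriptine: 10 − 4 = 6 h to 40 − 4 = 36 h.

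**Drug still present at the end of the visit.** Assume simple first-order decay from the 3 h peak, so that the fraction left 1 h later is 0.5^(1/half-life).
- Amisulpride: 0.5^(1/12) = 0.944, about 94% of peak.
- Bromocriptine: 0.5^(1/8) = 0.917 to 0.5^(1/2) = 0.707, about 71 to 92% of peak.

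**What follows each dose, by order (P = placebo, A = amisulpride, B = bromocriptine).** The orders are PAB, PBA, APB, ABP, BPA and BAP.

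| Drug | Next dose is placebo | Next dose is the other active drug | Last dose |
|---|---|---|---|
| Amisulpride | APB, BAP | PAB, ABP | PBA, BPA |
| Bromocriptine | ABP, BPA | PBA, BAP | PAB, APB |

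Placebo is last in ABP and BAP. Each treatment is therefore last in 2 of 6 orders. If allocation to the orders is equal, that is 44/3 = 14.7, about 15 of 44 completers per treatment with no scheduled symptom record after that visit. In another 2 of 6 orders a late symptom of an active drug, if entered on the next form, would count against placebo, and in 2 of 6 against the other active drug.

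**Search for other cover.** The general statements in sections 11, 15 and 16 set no between-visit time point, no look-back and no contact after Visit 3. Section 12 (Authorization procedures) sends adverse-event information from the study to the treatment programme; no flow in the other direction is described.

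**The case against.** The best reply is that the plan promises more than a checklist. Section 15 commits to asking participants how they feel for as long as they take part, section 11 says something similar, and section 16 names a medication effects log. So a reader who infers that side effects are recorded solely on visit days goes too far: spontaneous reports are not ruled out, and the log may do more than the text shows. Section 25 also does not say when in the visit the form is completed, so one cannot state that nothing is asked before the next dose, only that no look-back is specified.

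A reader might also infer that women have no contact of any kind after the last drug. For the patients the documents do not support this: section 15 places them in a closely supervised programme, and sections 11 and 12 describe a study physician with a clinical role there. The gap is clearest for healthy controls. But the supervision is mentioned in connection with suicidal ideation, and no route from programme observations to study data is described.

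Nor does section 25 limit the monthly report to checklist counts, so it cannot be said to rest wholly on incomplete data.

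Finally, 4/60 = 7% is a tempting measure of coverage. Five half-lives is the plan's elimination rule, not a window for side effects. The ratio weights hour 59 like hour 3, and the visit does cover both amisulpride peaks and the bromocriptine peak.

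Randomised order and an equal window for all three treatments balance the opportunity to record symptoms. They do not make the losses equal if late symptoms follow active drug more often than placebo. The documents give no rate for either, so a bias in the drug–placebo comparison is possible but not shown.

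**Conclusion.** The point stands as a gap in scheduled data collection. The one side-effect record with a defined time point closes at about 4 h, when by simple decay about 94% of peak amisulpride and 71 to 92% of peak bromocriptine remain. Nothing scheduled picks up later symptoms, assigns them to the dose they followed, or covers the time after Visit 3. Tolerability would tend to look better than it is.

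The number of events missed or misassigned is unknown, because the documents give no late-event rate. The decay figures rest on the stated half-lives and a single-exponential curve; they describe exposure, not symptom rates. The figure of one third of women per treatment assumes equal allocation to the six orders, which section 9 does not guarantee. The change is worth making before enrolment ends, since the information cannot be reliably recovered later.

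**What to change.** 1. At Visits 2 and 3, complete the existing checklist once more before dosing, asking about the time since the last visit. Enter the answers against that earlier visit, so that they count for its drug.
2. Add one call or message after Visit 3 with the same questions, timed to the plan's own 60 h.
3. State this collection window in section 15 (Data and Safety Monitoring Plan) and section 25 (Subject Level), and include these data in the monthly report. If the medication effects log in section 16 is meant to serve this purpose, say so and give its time points.

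The cost is two short repeats of an existing form per participant and about 44 brief contacts, all by existing staff, with some recall error for symptoms at home. The change concerns data collection alone.

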Contraindications: Amisulpride's use is contraindicated in the following disease states: Pheochromocytoma, concomitant prolactin-dependent tumors (e.g. breast cancer), movement disorders (e.g. Parkinson's Disease) and lactation. Subjects will be screened during the interview with the PI to ensure they do not have any of these conditions that are contraindicated.

Potential side effects during ongoing use include fever, excessive sweating, change in heart rate, chest pain, swelling, pain, and redness in the legs, increased frequency of infections, skin allergy, seizures, restless legs, twitches in the tongue and face, trembling, excessive salivation, constipation, decreased libido, weight gain, amenorrhea, gynecomastia, agitation and anxiety, tardive dyskinesia and neuroleptic malignant syndrome.

However, we will only include drug naïve individuals and the one-time application has been well tolerated in previous studies and we do not expect problems other than maybe nausea, which will be discussed as part of the IRB consent process (Rosenzweig et al., 2002).

Amisulpride has been used in similar ways in brain imaging research.

We expect to see if at all some nausea. The other side effects are in the context of prolonged prescription and not after single dose.

Subject Stopping criteria:

If a subject were to feel so nauseous she cannot perform the study it will be stopped. If there are any other symptoms that interferes with subjects' normal functioning we will stop the study.

Bromocriptine

Contraindications: This medication is contraindicated in syncopal migraines, uncontrolled hypertension, pheochromocytoma, prolactinoma, breast cancer, hypersensitivity/allergy to bromocriptine. Participants with a history of long QT syndrome or family history of sudden death or long QT syndrome will be exclusion criteria. A history of seizures or seizure disorder is an exclusion criterion. Subjects will be screened during the interview with the PI to ensure they do not have any of these conditions that are contraindicated.

Bromocriptine is a dopamine D2 receptor agonist for the treatment of Parkinson's Disease and Type 2 Diabetes.

The medication's potential common side effects for ongoing use as per the manufacturer include nausea, headache, stomach upset, dizziness, drowsiness, feeling faint, fainting, suddenly falling asleep. Serious side effects can include heart attack, stroke, pulmonary fibrosis.

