Individuals who ever took the medication before will be excluded, and the one-time application should at most be associated with nausea, headache or dizziness (Diederer et al., 2017). For each study participant only a one-time application is planned, just prior to brain imaging. The objective is to enhance dopamine transmission in the brain. We will only include drug naïve individuals and the one-time application has been well tolerated in previous studies and we do not expect problems other than maybe nausea, which will be discussed as part of the IRB consent process.

Bromocriptine has been used in similar ways in brain imaging research.

Subject Stopping criteria: If a subject were to feel so nauseous or dizzy that she cannot perform the study it will be stopped. If there are any other symptoms that interferes with subjects' normal functioning we will stop the study.

Study Duration

Altogether, assessments will take about 3 hours, the Pre-Scan blood draw and EKG will take about an hour and each brain imaging session including breakfast, medication administration and pre-scan questionnaires will take about 4 hours. Total study duration therefore is about 16 hours.

Clinical Procedures and Interventions: Not applicable, all procedures are research related, no standard of care procedures or treatment provided.

Drugs & Devices

Administration of Drugs: The drugs amisulpride (400 mg) and bromocriptine (1.25 mg) will be administered in study, 3 hours prior to the MRI scan. Both drugs are investigational drugs and the PI, [name], has submitted and received approval from the FDA for this study (IND # 141908, see attached approval letter)

Associated Devices:

- MRI scans will be performed on a GE Discovery MR 750 3.0 T Scanner (see attached 510(k) FDA approval document (**Discovery MR750 FDA Approval - K142361.pdf**))
- EKG will be performed at the Altman Clinical Trials Research Institute.

Research Facilities and Research Procedures Performed at Facility

1. **UC San Diego Health Eating Disorders Center for Treatment and Research:** PI/Research Staff offices, subject recruitment, data storage, data analysis, consent visits, storage of medication.
2. **Altman Clinical Trials Research Center (ACTRI):** Pre-Scan Visit (blood draw and EKG, primary option).
3. **Center for Advanced Laboratory Medicine (CALM):** Blood test processing (serum pregnancy test, BUN, Creatinine, Electrolytes).

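### Apart from nausea and heart rate, the scan-day record prompts for none of the amisulpride effects the protocol lists, although tolerability of amisulpride in AN is a study goal

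*Combined protocol and SAP*

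**What the plan says.** **The goal.** On the amisulpride dose, Section 9 (Dopamine Challenge Drugs) says: "Whether this dose is tolerable in an AN population has not been established and is a goal of this study". Aim 2 concerns feasibility and acceptability, and Section 15 counts side-effect assessment among the feasibility procedures.

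**The form.** Section 25 (Subject Level) states: "Research staff will complete symptom checklist on each Study Visit day". The items given are a "symptom checklist including: nausea, headache, dizziness, tiredness, other". The same entry requires "Documentation of blood pressure & heart rate pre-medication administration and post scan".

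**Amisulpride effects.** The amisulpride safety text in Section 9 begins "Potential side effects during ongoing use include fever, excessive sweating, change in heart rate, chest pain" and continues with, among others, "restless legs, twitches in the tongue and face, trembling, excessive salivation, constipation, decreased libido, weight gain, amenorrhea, gynecomastia, agitation and anxiety". It then says that nausea is what might be seen after the single study dose, and assigns the other effects to prolonged prescription. Section 14 likewise expects only nausea.

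**Bromocriptine effects.** Section 9 lists eight common effects, also for ongoing use, and says that "the one-time application should at most be associated with nausea, headache or dizziness".

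**Other routes to the record.** Section 15 has staff assess well-being after dosing and ask how participants feel and whether they have problems. The Section 9 assessment table includes a Post MRI Questionnaire and the PANAS mood scale. Section 16 mentions a Subject Medication Effects Log without describing its contents.

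**The concern.** A symptom asked about by name is usually recorded more completely than one that must be volunteered or happen to be seen. Here the named items fit one active drug better than the other. The gap falls on motor and arousal effects of amisulpride, the drug whose tolerability in this population the protocol calls unestablished.

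Two uses of the data are affected. The first is the tolerability result. The second is safety review: Section 25 bases the decision on whether the study is safe to continue on monthly aggregate adverse-event reports, and Section 15 says there is no independent monitoring board. A smaller point is that restlessness or trembling may move the head in the scanner. Motion itself is measured and modelled, but without symptom data a poor scan would be harder to attribute to a drug effect.

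**Working it through.** The plan gives no figure to reproduce on this point. The check is an item-by-item comparison of the form with the protocol's own lists.

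**Inputs**
- Named items (Section 25): nausea, headache, dizziness, tiredness; 4 in all, plus 'other'.
- Bromocriptine common effects for ongoing use (Section 9): 8.
- Amisulpride effects for ongoing use (Section 9): about 21, counting leg swelling, pain and redness as one and agitation and anxiety as two.
- Single-dose expectations (Section 9): for bromocriptine at most nausea, headache or dizziness; for amisulpride at most nausea.

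**Overlap**

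| Comparison | Bromocriptine | Amisulpride |
|---|---|---|
| Named items found in the ongoing-use list | 3 of 4 word for word; 4 of 4 if tiredness is read as drowsiness | 0 of 4 |
| Single-dose expected effects that are named items | 3 of 3 | 1 of 1 (nausea) |
| Ongoing-use effects measured outside the checklist on scan days | not counted | 1 of about 21 (heart rate) |

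The form covers both drugs if the single-dose expectation is right. It is thin for amisulpride if that expectation is wrong.

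**Is the single-dose expectation enough to settle the item list?** Two passages in Section 9 pull apart. The safety text sets the long amisulpride list aside as belonging to prolonged use. The dosing text says tolerability in AN is not established and is to be learned here. Choosing items from the expectation alone assumes part of the answer. The limit is also not applied evenly: bromocriptine's eight effects are given for ongoing use too, yet drowsiness, which is not among its single-dose expectations, is in effect asked about as tiredness.

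**Which unprompted effects are relevant?** Each scan visit lasts about 4 hours (3 before the scan, 1 in it), with dosing 3 hours before the scan. Of the listed amisulpride effects, seven could be noticed by the participant or staff in that time if they occurred: agitation, anxiety, sweating, salivation, trembling, twitches and restless legs. That selection is a judgement; the documents do not say these effects occur after one dose.

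**Size, for scale only.** The documents give no event or capture rates. Assume 20 women with AN (the group size in the Statistical Power paragraph), a true incidence p, and a probability s that an occurring symptom is recorded. The chance of recording at least one case is 1 − (1 − p·s)^20:

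| p | s = 1 | s = 0.5 | s = 0.25 |
|---|---|---|---|
| 0.05 | 0.642 | 0.397 | 0.222 |
| 0.10 | 0.878 | 0.642 | 0.397 |
| 0.20 | 0.988 | 0.878 | 0.642 |

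For example, with p = 0.10 and s = 0.5: 1 − 0.95^20 = 0.642. In a group this small, incomplete capture can decide whether an effect is seen at all. Neither p nor s is known, so this is not an estimate of the shortfall.

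**The case against.** The strongest reply is that the form matches what the protocol expects. Nausea, the only effect foreseen after one amisulpride dose, is its first item, and heart rate is recorded. Long-term effects such as weight gain, amenorrhea and gynecomastia have no place on a same-day form. Staff complete the checklist, so visible trembling or sweating can be entered without the woman volunteering it. General questions, the Post MRI Questionnaire and the PANAS offer further routes. The wording of the item list leaves room for more items, and the Medication Effects Log may hold them. Symptoms that interfere with normal functioning stop the study for either drug, so severe intolerance should surface regardless.

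Most of this stands, and it rules out three stronger readings that a reader might infer:
- *That no amisulpride effect is captured.* Nausea is prompted and heart rate is measured.
- *That the two drugs are assessed by different procedures.* The same form is used on every scan day, under both drugs and placebo. The imbalance lies only in which effects are prompted.
- *That amisulpride will look better tolerated by some calculable margin.* That would need assumed event and capture rates, and would have to treat all amisulpride symptoms as unprompted, which nausea contradicts. Aims 1 and 2 also take each drug separately; no drug-versus-drug tolerability comparison is planned.

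What the reply does not answer is that a stated tolerability goal in a new population is served by asking about mild and moderate effects directly. The stopping rule catches only those that interfere with functioning, and neither the PANAS nor any other instrument with stated items asks about motor symptoms.

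**Conclusion.** The point holds in limited form, as a cheap improvement. Apart from nausea and heart rate, no amisulpride effect on the protocol's own list is prompted by name; the remaining named items follow bromocriptine's list. Seven listed effects that could be noticed within a visit depend on 'other', staff observation or general questions, so their capture is likely to be less complete. The amount cannot be calculated from the documents.

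This rests on two assumptions: that the four named symptoms are the full set of prompts, and that prompted symptoms are recorded more completely than unprompted ones. If the Medication Effects Log already contains the missing items, only a cross-reference is needed.

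**What to change.** In Section 25 (Subject Level), add to the same checklist, at all three visits whatever the drug, these effects from the protocol's own lists: restless legs or restlessness, twitches, trembling, salivation, sweating, agitation or anxiety, stomach upset, and feeling faint. Keep 'other'. State that prompted symptoms will be reported by drug and placebo, separately from volunteered ones. If the Medication Effects Log in Section 16 already holds these items, cite it in Section 25 instead.

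Prompted amisulpride ongoing-use effects would rise from 0 to 7 of about 21 (agitation and anxiety counted separately), with heart rate measured as an eighth. Bromocriptine coverage would rise from 4 to 6 of 8 (4 + stomach upset + feeling faint, with tiredness read as drowsiness).

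The cost is a revised one-page form and about one more minute per visit. A few more mild symptoms will be recorded, on placebo days too; the placebo day gives the background rate for reading them. No dose, visit or stopping rule changes.
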